6.1.8 Data Monitoring Committee

The Data Monitoring Committee (DMC) will review safety data intermittently according to the DMC charter. Details of the DMC review are presented in the DMC charter. The DMC charter has been created to provide detailed descriptions of the schedule of analyses

and the DMC meetings. DMC membership, responsibilities and the description of the data coordinating center are documented in the charter.

6.1.9 Toxicity Management

6.1.9.1 Prophylaxis and Management of Tumor Lysis Syndrome

Venetoclax can cause rapid reduction in tumor and thus poses a risk for TLS in the initial 5-week dose-titration phase. Changes in electrolytes consistent with TLS that require prompt management can occur as early as 6 to 8 hours following the first dose of venetoclax and at each dose increase.

Risk Assessment for tumor lysis syndrome: The risk of TLS is a continuum based on multiple factors, including tumor burden and comorbidities. Subjects with high tumor burden (e.g., any lymph node with a diameter ≥ 5 cm or high absolute lymphocyte count [ALC $> 25 \times 10^9/L$]) are a greater risk of TLS. Reduced renal function (estimated creatinine clearance [eCrCl] < 80 mL/min) further increases the risk. The risk may decrease as tumor burden decreases with venetoclax treatment.

Additional comorbidities may further increase the risk for TLS.

Prior to initiating venetoclax, tumor burden assessment, including radiographic evaluation (e.g., refer to Section 5.3.1.1 Study Procedures – Disease Assessment) must be performed for all subjects during Screening. The full blood chemistry/hematology panel (refer to Table 4 Clinical Laboratory Tests) should be performed in all subjects during the Screening period in order to assess eligibility and to correct pre-existing abnormalities.

If the full chemistry/hematology panel was assessed more than 72 hours prior to the 1st dose of venetoclax, an additional full lab panel should be performed and reviewed within 72 hours prior to dosing in order to make a treatment decision.

Prophylaxis for tumor lysis syndrome: The prophylaxis measures listed below should be followed. More intensive measures (including hospitalization) should be employed as overall risk increases:

Hydration: Subjects should be adequately hydrated prior to starting treatment with venetoclax and during the dose-titration phase. The recommended volume is 1.5 to 2.0 L (approximately 6 to 8 glasses) of water each day. Subjects should be instructed to drink water starting 2 days before and on the day of the first dose, and every time the dose is increased. Intravenous (IV) fluids should be administered as indicated based on overall risk of TLS or for those who cannot maintain an adequate level of oral hydration. For subjects for whom volume overload is considered a significant risk, hospitalization should be considered.

Anti-hyperuricemic agents: Anti-hyperuricemic agents should be administered 2 to 3 days prior to starting treatment with venetoclax and may be continued through the titration phase.

Laboratory Assessments:

PRE-DOSE LABS:

Prior to the initial dose of venetoclax:

- During the Screening Period: For all subjects, the chemistry/hematology panel (see [Table 4](#) Clinical Laboratory Tests) is required.
 - Pre-existing abnormalities should be corrected.
- Within 72 hours of Week 1/Day 1: If the screening labs were more than 72 hours before the planned first dose, the chemistry/hematology panel should be repeated. These results should be reviewed before dosing.
 - Labs should be assessed and pre-existing abnormalities should be corrected.
- On the day of Week 1/Day 1: Before dosing, the chemistry/hematology panel should be drawn. The results of the labs drawn on Week 1 Day 1 need to be reviewed prior to dosing **IF** an additional lab within 72 hours of the initial dose at Week 1 Day 1 was not drawn **AND** reviewed.

Prior to each subsequent dose increase, for all subjects:

- Within 72 hours of each subsequent dose increase: The chemistry/hematology panel should be repeated. The results should be reviewed prior to dose increasing.
- Prior to dosing, on the day of each subsequent dose increase: Before dosing, the chemistry/hematology panel should be drawn. The results of the labs drawn on Day 1 of each dose increase need to be reviewed prior to dosing **IF** an additional lab draw within 72 hours of the dose increase was not drawn AND reviewed.

POST-DOSE LABS:

For all subjects, the chemistry/hematology panel (refer to Table 4 Clinical Laboratory Tests) should be monitored at 6 to 8 hours and at 24 hours* after the first dose of venetoclax (20 mg) and after the first dose increase (50 mg). Electrolyte abnormalities should be corrected promptly. The next venetoclax doses (Day 2 20 mg venetoclax dose and Day 2 50 mg venetoclax dose) should not be administered until the 24-hour* lab results have been evaluated. Electrolyte abnormalities should be corrected promptly. For subjects who continue to be at risk of TLS, the same lab monitoring schedule (i.e., 6 to 8 hour and 24-hr post dose) should be followed at the subsequent dose increases.

This monitoring is also recommended during the re-initiation of the therapy after a dose interruption.

*All 24 hour post-dose laboratory assessments may be taken within a 2 hour window, if necessary.

Hospitalization: Based on investigator assessment, some subjects, especially those at greater risk of TLS may require hospitalization on the day of the first dose of venetoclax for more intensive prophylaxis and monitoring through the first 24 hours. Hospitalization should be considered for subsequent dose increases based on reassessment of risk.

6.1.9.2 Dose Modifications Based on Toxicities

Dosing interruption and/or dose reduction may be required. See [Table 7](#) for dose modifications for hematologic and other toxicities related to venetoclax. For subjects who have had a dosing interruption greater than 1 week during the first 5 weeks of dose titration or greater than 2 weeks when at the daily dose of 400 mg, TLS risk should be reassessed to determine if restarting at a reduced dose is necessary (e.g., all or some levels of the dose titration).

Tumor Lysis Syndrome

If a subject experiences blood chemistry changes suggestive of TLS, the following day's venetoclax dose should be withheld. If resolved within 24 to 48 hours of last dose, treatment with venetoclax can be resumed at the same dose. For events of clinical TLS or blood chemistry changes requiring more than 48 hours to resolve, treatment should be resumed at a reduced dose ([Table 7](#) and [Table 8](#)). When resuming treatment with venetoclax after interruption due to TLS, the instructions for Prophylaxis for tumor lysis syndrome should be followed.

Other Toxicities

Treatment with venetoclax should be withheld for any grade 3 or 4 non-haematological, grade 3 or 4 neutropenia with infection or fever, or grade 4 haematological toxicities, except lymphopenia. To reduce the risk of infection associated with neutropenia, granulocyte-colony stimulating factor (G-CSF) may be administered with venetoclax if clinically indicated. Once the toxicity has resolved to grade 1 or baseline level (recovery), therapy with venetoclax may be restarted at the same dose. If the toxicity recurs, and for any subsequent occurrences, the dose reduction guidelines in [Table 7](#) and [Table 8](#) should be followed when resuming treatment with venetoclax following resolution. A larger dose reduction may occur at the discretion of the investigator. For subjects who require dose reductions to less than 100 mg for more than 2 weeks, due to adverse events, discontinuation of venetoclax should be considered.

Table 7. Recommended Dose Modifications for Toxicities

Event	Occurrence	Action
Tumor Lysis Syndrome		
Blood chemistry changes or symptoms suggestive of TLS	Any	Withhold the next day's dose. If resolved within 24 – 48 hours of last dose, resume at the same dose.
		For any blood chemistry changes requiring more than 48 hours to resolve, resume at a reduced dose (Table 8)
		For any events of clinical TLS, ^a resume at a reduced dose following resolution (Table 8).
Non-Hematologic Toxicities		
Grade 3 or 4 non-hematologic toxicities	1 st occurrence	Interrupt venetoclax Once the toxicity has resolved to Grade 1 or baseline level, venetoclax therapy may be resumed at the same dose. No dose modification is required.
	2 nd and subsequent occurrences	Interrupt venetoclax. Follow dose reduction guidelines in Table 8 when resuming treatment with venetoclax after resolution. A larger dose reduction may occur at the discretion of the investigator.
Hematologic Toxicities		
Grade 3 or 4 neutropenia with infection or fever; or Grade 4 hematologic toxicities (except lymphopenia)	1 st occurrence	Interrupt venetoclax. To reduce the infection risks associated with neutropenia, granulocyte-colony stimulating factor (G-CSF) may be administered with venetoclax if clinically indicated. Once the toxicity has resolved to Grade 1 or baseline level, venetoclax therapy may be resumed at the same dose.
	2 nd and subsequent occurrence	Interrupt venetoclax. Consider using G-CSF as clinically indicated. Follow dose reduction guidelines in Table 8 when resuming treatment with venetoclax after resolution. Additional dose reductions may occur at the discretion of the physician.
Consider discontinuing venetoclax for subjects who require dose reductions to less than 100 mg for more than 2 weeks.		

a. Clinical TLS was defined as laboratory TLS with clinical consequences such as acute renal failure, cardiac arrhythmias or sudden death and/or seizures.

Note: Adverse reactions were graded using NCI CTCAE version 4.03.

Table 8. Dose Modification for Toxicity During Venetoclax Treatment

Dose at Interruption, mg	Restart Dose, mg ^a
400	300
300	200
200	100
100	50
50	20
20	10

a. During the dose titration phase, continue the reduced dose for 1 week before increasing the dose.

Dose Modifications for use with CYP3A Inhibitors

Concomitant use of venetoclax with strong or moderate CYP3A inhibitors increases venetoclax exposure and may increase the risk for TLS at initiation and during the dose-titration phase. Concomitant use of venetoclax with strong CYP3A inhibitors at initiation and during the dose-titration phase is contraindicated.

Concomitant use of venetoclax with moderate CYP3A inhibitors at initiation and during the dose-titration phase should be avoided. Alternative treatments should be considered. If a moderate CYP3A inhibitor must be used, the initiation and titration doses of venetoclax should be reduced by at least 50%. Subjects should be monitored more closely for signs of toxicities.

For subjects who have completed the dose-titration phase and are on a steady daily dose of venetoclax, the venetoclax dose should be reduced by at least 50% when used concomitantly with moderate CYP3A inhibitors and by at least 75% when used concomitantly with strong CYP3A inhibitors. Subjects should be monitored more closely for signs of toxicities. The venetoclax dose that was used prior to initiating the CYP3A inhibitor should be resumed 2 to 3 days after discontinuation of the CYP3A inhibitor.

Missed Dose

If a subject misses a dose of venetoclax within 8 hours of the time it is usually taken, the subject should take the missed dose as soon as possible and resume the normal daily dosing schedule. If a subject misses a dose by more than 8 hours, the subject should not take the missed dose and should resume the usual dosing schedule the following day.

If a subject vomits following dosing, no additional dose should be taken that day. The next prescribed dose should be taken at the usual time the following day.

6.1.9.3 Management of Neutropenia

Nonclinical and clinical experience indicates that venetoclax may cause neutropenia. Subjects with a history of neutropenia who have received multiple prior therapies and/or have significant bone marrow involvement may be at a particularly high risk.

Grade 3 or 4 neutropenia has been reported in subjects treated with venetoclax. Complete blood counts should be monitored throughout the treatment period. Dose interruptions or dose reductions are recommended for subjects with severe neutropenia. Supportive measures including antimicrobials for any signs of infection and prophylactic use of growth factors (e.g., G-CSF) should be considered.

6.1.9.4 Immunization

Live attenuated vaccines should not be administered prior to, during, or after treatment with venetoclax until B-cell recovery occurs. The safety and efficacy of immunization with live attenuated vaccines during or following venetoclax therapy have not been studied. Subjects should be advised that vaccinations may be less effective.

6.1.9.5 Management of Hematologic Toxicities Other Than Neutropenia or Lymphopenia

Venetoclax treatment should be withheld for any Grade 4 hematologic toxicity. Once the toxicity has resolved to Grade 1 or baseline level (recovery), venetoclax may be re-started at the same dose. If the toxicity recurs, the dose reduction guidelines in [Table 8](#) should be

followed when resuming study treatment following resolution. Additional dose reductions may occur at the discretion of the physician.

6.1.9.6 Management of Non-Hematologic Toxicity

Venetoclax treatment should be withheld for any clinically relevant \geq Grade 3 non-hematologic toxicity. Once the toxicity has resolved to Grade 1 or baseline level (recovery), venetoclax may be re-started at the same dose. If the toxicity recurs, the dose reduction guidelines in [Table 8](#) should be followed when resuming study treatment following resolution. Additional dose reductions may occur at the discretion of the physician.

6.2 Product Complaint

6.2.1 Definition

A Product Complaint is any Complaint (see Section [6.0](#) for the definition) related to the biologic or drug component of the product.

For a product this may include, but is not limited to, damaged/broken product or packaging, product appearance whose color/markings do not match the labeling, labeling discrepancies/inadequacies in the labeling/instructions (example: printing illegible), missing components/product, or packaging issues.

Any information available to help in the determination of causality to the events outlined directly above should be captured.

6.2.2 Reporting

Product Complaints concerning the investigational product must be reported to the Sponsor within 24 hours of the study site's knowledge of the event by entering the product complaint in RAVE, the EDC system. If the EDC system is not operable, the Product Complaint Form should be used and emailed to: [contact] **within 24 hours** of the study site's knowledge of the event. Product Complaints occurring during

the study will be followed-up to a satisfactory conclusion. All follow-up information is to be reported to the Sponsor (or an authorized representative) and documented in source as required by the Sponsor. Product Complaints associated with adverse events will be reported in the study summary. All other complaints will be monitored on an ongoing basis.

Product Complaints may require return of the product with the alleged complaint condition. In instances where a return is requested, every effort should be made by the investigator to return the product within 30 days. If returns cannot be accommodated within 30 days, the site will need to provide justification and an estimated date of return.

The description of the complaint is important for AbbVie in order to enable AbbVie to investigate and determine if any corrective actions are required.

8.0 Statistical Methods and Determination of Sample Size

8.1 Statistical and Analytical Plans

Analyses will be performed on all subjects enrolled into the study, unless otherwise specified. The date of enrollment is defined as the date that the Interactive Response Technology (IRT) provided a subject number.

Safety analyses will be performed on all subjects who receive at least one dose of venetoclax.

Detailed analysis descriptions will be provided in a separate statistical analysis plan.

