If a subject has an ongoing AE or an unresolved clinically significant laboratory result 30 days following last dose of study drug, the site will attempt to provide follow-up until the AE has resolved to a \leq Grade 1 or baseline or it is the investigator's judgment that the event is unlikely to resolve.

Additionally, CT or MRI scans are not required, however if collected by the site as standard of care, the data should be recorded in EDC.

Post-Treatment and Survival Assessments

After treatment discontinuation, subjects will be followed for disease progression (if progression has not already occurred) and survival. Post-treatment calls will be performed every 6 months until discontinuation from the study. Survival information (i.e., the date and cause of death, post-treatment cancer therapies, date of progression etc.) will be collected. This period will continue for 2 years following discontinuation of venetoclax.

Extended Access Phase

In countries where venetoclax is not commercially available, subjects who continue to derive benefit after 2 years of treatment may be able to extend their treatment for up to 2 additional years. AbbVie will work with the investigator on a case by case basis to consider the potential continuation of venetoclax therapy. The Extended Access Visits will include:

- Collection of Survival information
- AE/SAE/Con Med assessment
- Study drug reconciliation and dispensing

All other procedures should be performed as standard of care. The specific study assessments to be performed during these visits are detailed in Appendix E Study Activities.

Assignment of Subject Numbers

Subjects will be assigned unique consecutive subject numbers at screening, as described in Section 5.5.3. The results of all screening evaluations must be within clinically acceptable limits, upon review by the investigator before a subject can be administered

study drug. Subjects will not be enrolled in the study if laboratory or other screening results are unacceptable.

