5.5.3 Method of Assigning Subjects to Treatment Groups

All subjects are assigned to the same treatment group in this single arm study. Subjects will be allocated a unique consecutive subject number at Screening. Subject numbers will consist of 5 digits (XXX01), with the first three digits denoting site number and the last 2 digits as the subject number, beginning with 01. All subjects will be enrolled using an Interactive Response Technology (IRT). Before the study is initiated, each site will be provided with the IRT user instructions, which provides direction on how to use the IRT via the Web or the telephone. Since this is an open-label study, subjects will maintain the same subject number regardless of the number of re-screens and through the duration of the study. The site, in conjunction with the Sponsor, will be responsible for assignment of all unique subject numbers at Screening and dose assignments if the subject is not a screening failure.

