Time to progression (TTP) will be defined as the number of days from the date of first dose or enrollment if not dosed to the date of earliest disease progression. All disease progression will be included regardless whether the event occurred while the subject was taking the study drug or had previously discontinued the study drug. If the subject does not experience disease progression, then the data will be censored at the date of last available disease assessment. Data for subjects who receive non-protocol, CLL therapy prior to disease progression will be censored at the last disease assessment prior to receiving non-protocol therapy. Data for subjects without any disease assessments performed after the baseline visit will be censored at the time of enrollment plus 1 day. TTP will be analyzed by Kaplan-Meier methodology using data for all subjects enrolled. Median time TTP will be calculated and 95% confidence interval for median time TTP will be presented.

Progression-free survival (PFS) will be defined as the number of days from the date of first dose to the date of earliest disease progression or death. All disease progression will be included regardless whether the event occurred while the subject was taking the study drug or had previously discontinued the study drug. If the subject does not experience disease progression or death, then the data will be censored at the date of last disease

assessment. Data for subjects who receive non-protocol, CLL therapy prior to disease progression will be censored at the last disease assessment prior to receiving non-protocol therapy. Data for subjects without any disease assessments performed after the baseline visit will be censored at the time of enrollment plus 1 day. PFS will be analyzed by Kaplan-Meier methodology using data for all subjects enrolled. Median time PFS will be calculated and 95% confidence interval for median time PFS will be presented.

Overall survival (OS) will be defined as number of days from the date of first dose to the date of death for all dosed subjects. For subjects who did not die, their data will be censored at the date of last study visit or the last known date to be alive, whichever is later. OS will be analyzed by Kaplan-Meier methodology using data from all enrolled subjects. Median time survival will be estimated and 95% confidence interval for the median time survival will be presented.

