5.0 Analysis Populations

5.1 Definition for Analysis Populations

5.1.1 Quality of Life, Efficacy, and Safety Populations

All enrolled subjects who receive at least one dose of venetoclax will be included in this analysis unless otherwise specified.

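### Protocol 8.1 and 8.1.2.2 tie censoring and the analysis set to an enrolment date fixed at Screening, giving zero or negative TTP/PFS times and a denominator that differs from the dosed set in the synopsis and SAP

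*Protocol*

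**What the plan says.** **Enrolment date.** Protocol 8.1: "The date of enrollment is defined as the date that the Interactive Response Technology (IRT) provided a subject number". Protocol 5.5.3: "Subjects will be allocated a unique consecutive subject number at Screening", and "subjects will maintain the same subject number regardless of the number of re-screens". Section 5.3.1.1 repeats the timing ("Subjects will be assigned unique consecutive subject numbers at screening") but adds: "Subjects will not be enrolled in the study if laboratory or other screening results are unacceptable". Screening takes place within the 28 days before the first dose (Protocol 5.1).

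**Censoring.** Protocol 8.1.2.2 states, for both TTP and PFS: "Data for subjects without any disease assessments performed after the baseline visit will be censored at the time of enrollment plus 1 day". PFS starts at the first dose; TTP starts at the first dose, or at enrolment for a subject never dosed. For DOR, subjects who never respond are censored on the enrolment date. SAP 10.1.2 instead censors TTP and PFS at first dose plus one day and restricts DOR to responders.

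**Population.** Protocol 8.1 analyses all enrolled subjects by default and limits only the safety analyses to dosed subjects. The synopsis uses subjects with at least one dose unless the SAP says otherwise. SAP 5.1.1: "All enrolled subjects who receive at least one dose of venetoclax will be included in this analysis unless otherwise specified".

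**The concern.** A time-to-event variable cannot be censored before its own origin. The protocol takes the origin from the first dose and the censoring date from an event at Screening, so the derived time can be zero or negative. The first scheduled on-study disease assessment is Week 24 (Protocol 5.3.1.1 and Appendix D). The rule therefore reaches dosed subjects who leave before then with no assessment and no progression or, for PFS, death.

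The same term also decides who is analysed. Two documents that govern the same endpoints give different sets, and the protocol disagrees with its own synopsis. For ORR and CR the set is the denominator of the reported rate.

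**Working it through.** **1. The plan's own figure.** Inputs from Protocol 8.2: SD 20.5, difference 5, one-sided alpha 0.025, power 90%. One-sample normal approximation: n = (20.5 × (1.960 + 1.282) / 5)² = 176.6, rounded up to 177. This reproduces the stated number. The 200 are explicitly subjects to be dosed, so 177/200 implies an 11.5% drop-out allowance. The definition of enrolment does not enter this calculation.

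**2. Censored time with no post-baseline assessment.** Let the subject number be issued k days before the first dose, and use the SAP 10.1.2 formula: time = censoring date − first dose date + 1.

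- Protocol rule: the censoring date is first dose − k + 1, so time = (−k + 1) + 1 = 2 − k.
- SAP rule: the censoring date is first dose + 1, so time = 1 + 1 = 2.

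| k (days) | Protocol rule | SAP rule |
|---|---|---|
| 0 | 2 | 2 |
| 2 | 0 | 2 |
| 7 | −5 | 2 |
| 14 | −12 | 2 |
| 28 | −26 | 2 |

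Without the +1 convention each protocol value is one day lower, so −27 at k = 28. A re-screened subject keeps the number, and Protocol 5.3.1.1 sets no upper limit on the interval, so k can exceed 28.

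**3. DOR.** Under Protocol 8.1.2.2, DOR starts at first response. A never-responder has no start date, so censoring at enrolment gives no defined duration.

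**4. Populations side by side.**

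| Place | Set |
|---|---|
| Synopsis, Statistical Methods | At least one dose, unless the SAP differs |
| Protocol 8.1 | All enrolled; safety only in dosed |
| Protocol 8.1.2.2, ORR and CR | None named, so the 8.1 default applies |
| Protocol 8.1.2.2, DOR, TTP, PFS | All enrolled; the TTP origin provides for undosed subjects |
| Protocol 8.1.2.2, OS | Defined for dosed, analysed in all enrolled |
| SAP 5.1.1 | Enrolled and dosed |
| SAP 10.1.2, DOR | Responders only |
| SAP 10.2.2, DOR | All subjects in 5.1.1 |

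An eligible subject who is enrolled but never dosed is in the protocol's set and outside the SAP's on any reading. PFS and OS have no time origin for that subject.

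**5. Effect on the Kaplan-Meier estimate.** A subject censored at or before time 0 is in no risk set. A subject censored at time 2 is in the risk set only for events at times 1 and 2. The two rules therefore give the same curve unless a progression or death falls in those first two days. Never-responders censored at enrolment for DOR likewise enter no risk set.

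**The case against.** The strongest reply is that the SAP already settles the matter. Protocol 8.1 defers detail to it, the synopsis yields to it, and it has the dosed population, first-dose censoring and responder-only DOR. Early censoring also barely touches the Kaplan-Meier curve (step 5 above). Both points stand, and they make this a consistency correction, not a source of bias in the planned estimates. They do not make the protocol text valid, and the SAP is not fully consistent itself, because 10.2.2 sends DOR back to the whole 5.1.1 set.

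Three stronger readings are tempting.

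- **Screen failures are in the protocol's analysis set.** Section 8.1 read with 5.5.3 could be taken that way, since screen failures hold numbers. But 8.1 defines a date, not membership, and 5.3.1.1 says subjects with unacceptable screening results are not enrolled. The supportable statement is that the protocol does not reconcile the two.
- **Response rates would be heavily diluted.** If 10% to 30% of numbered subjects failed screening, 200 dosed would correspond to 200/0.9 = 222 up to 200/0.7 = 286 numbered. An ORR of 81.7% (the Study M12-175 expansion cohort, Protocol 3.0) would then read 73.5% down to 57.2%. The failure rates are pure assumption, the result needs the reading just rejected, and no SAP analysis uses that denominator.
- **The data cutoff in Protocol 8.1.3 could hang on a screen failure.** It could not. The rule requires Week 48 assessments to be completed or all subjects to have stopped venetoclax, and a screen failure can do neither.

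**Conclusion.** The point holds as a conflict of wording with limited numerical reach. Under the protocol text, TTP and PFS for early leavers are zero or negative whenever the number precedes dosing by two or more days, down to −26 days at the 28-day limit, against +2 days in the SAP. Such values are not usable in a Kaplan-Meier analysis, and a programmer would have to drop or override them. DOR is undefined for never-responders. ORR and CR have two denominators, which differ by at least the enrolled but undosed subjects; the documents do not say how many there will be.

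Medians are essentially unchanged, and the primary endpoint's sample size stands. The conclusion assumes that the number issued at Screening is the one Section 8.1 refers to; the documents describe only one subject number. The day counts use the SAP's +1 convention.

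**What to change.** In Protocol 8.1 and 8.1.2.2:

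- State that quality-of-life and efficacy analyses use subjects with at least one dose of venetoclax, as in the synopsis and SAP 5.1.1.
- For TTP and PFS with no post-baseline assessment, replace enrolment plus one day with first dose plus one day, as in SAP 10.1.2.
- Limit DOR to responders, as in SAP 10.1.2, and remove the enrolment-date censoring of never-responders. Align SAP 10.2.2 with this.
- Stop treating the date of the Screening subject number as the date of enrolment, and reconcile 8.1 with the statement in 5.3.1.1 on who is not enrolled. The new definition should not rest on an IRT eligibility-confirmation date, because the documents describe none.

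The cost is wording only. The three analysis rules are ones the sponsor has already written, the first dose date is already the time origin, and no sample-size figure changes.
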